3. Research Proposal

TITLE OF RESEARCH PROPOSAL

Feasibility Randomised Controlled Trial of Intensive Music Therapy on Cognitive Function in Subacute Stroke Rehabilitation in Malaysia

KEY WORDS

Music therapy; randomised controlled trial; rehabilitation; stroke; cognition; attention

BACKGROUND/ JUSTIFICATION

Stroke is a leading cause of long-term disability worldwide, often resulting in cognitive impairments, particularly in memory, attention, and executive function, which significantly impact patients' quality of life and daily functioning. Research indicates that music therapy can enhance cognitive recovery during neurorehabilitation by engaging multiple brain networks and promoting neuroplasticity. There is still limited evidence on the specific effects of intensive music therapy during the subacute phase, a critical period for neurorehabilitation. In addition, there is no published report on the efficacy of structured music therapy as part of a cognitive rehabilitation program in Malaysia, despite a concerted move to promote the use of music for therapeutic purposes in this country over the last decade. Music therapy has not been a part of a formal therapeutic modality in most neurorehabilitation program locally, unlike the more established music therapy practice in neighbouring countries such as Singapore. This study proposes to investigate the effects of intensive music therapy on cognitive functions in subacute stroke patients, while also assessing its feasibility within regular rehabilitation program in Malaysian setting. If successful, this approach could support the integration of music therapy into clinical neurorehabilitation settings, promoting its wider use for cognitive recovery post-stroke.

OBJECTIVES/OUTCOMES

Objectives:

- 1. To assess the feasibility of recruiting, retaining, and ensuring adherence of subacute stroke patients to an intensive music therapy program within a neurorehabilitation setting.
- 2. To evaluate the practicality of integrating music therapy into existing stroke rehabilitation protocols, including the training requirements for staff, resource availability, and logistical considerations.
- 3. To gather preliminary data on the impact of intensive music therapy on cognitive function, specifically memory, attention, and executive function, to estimate effect sizes and inform the design of a larger, fully powered randomized controlled trial.

Expected outcomes:

- 1. The study successfully recruits and retains the target number of subacute stroke patients, with a high adherence rate to the intensive music therapy sessions.
- 2. The intervention is effectively integrated into the existing stroke rehabilitation program, with staff adequately trained and resources efficiently utilized.
- 3. Preliminary data show trends of improvement in cognitive functions (e.g., memory, attention, executive function) among patients receiving music therapy

METHODOLOGY

Study design

This study will be a feasibility randomised controlled trial (RCT) in one centre, with two parallel groups: an intervention group receiving intensive music therapy in addition to standard neurorehabilitation, and a control group receiving only standard neurorehabilitation. A certified music therapist will conduct the intervention and a trained assessor will evaluate the outcome. The assessor is blinded to the patients' allocation group and will evaluate the cognitive outcomes at baseline, at two weeks (after 8 sessions) and at 1 month post intervention. All patients who

are admitted to the rehabilitation ward for stroke rehabilitation will be screened and approached. Informed consent will be obtained from eligible patients before randomisation.

To ensure that there are exactly 15 patients in both the control and intervention groups, block randomization will be used using a random number generator. After randomization, the group assignments will be kept in a password-protected file that only the study coordinator can access. The assessor will not have access to this information because the patients will be labelled with anonymous codes that do not reveal whether they are in the control or intervention group. The assessor will only know the code, not the group assignment, ensuring unbiased evaluation.

Intervention group

The music therapy session described follows a structured and engaging approach, aimed at enhancing the patient's cognitive skills during neurorehabilitation. Here's a summary of the session components:

1. Relaxation Phase: The session begins with a five-minute deep breathing exercise to help the participant relax and prepare mentally for the activity.

2. Song Selection: The therapist presents a list of 50 well-known pop songs from the past three decades, available in four languages (Malay, English, Mandarin, and Tamil). The participant chooses a song based on personal preference, promoting cultural relevance and personal connection.

3. Instrument Selection and Familiarization: The therapist offers five percussion instruments (kompang, djembe, tambourine, maracas, shaker) for the participant to explore. The participant selects one instrument to accompany the chosen song.

4. Rhythmic Training: The participant learns to play a rhythmic pattern that complements the song. Once mastered, they sing along with the therapist while playing the rhythm.

5. Progression and Adjustment: If the participant successfully plays the rhythm for over 50% of the song duration, they are invited to choose another song and instrument. If struggling, they are prompted to select another song to prevent frustration. Rest breaks are included, and the therapist adjusts the session based on the participant's endurance.

6. Session Frequency: Each session lasts 45 minutes and is conducted four times a week for two weeks, integrated with the patient's standard neurorehabilitation.

7. Customization: The therapist tailors the sessions according to the patient's preferences, medical condition, and emotional state, with real-time adjustments based on feedback and continuous coordination with the rehabilitation team.

This individualized approach aims to enhance patient engagement and recovery by integrating music, rhythm, and therapeutic interaction into the neurorehabilitation process.

Control group

In the control group, participants will receive the standard neurorehabilitation program prescribed by the rehabilitation team, without the addition of music therapy. This will provide a baseline to compare outcomes with the intervention group and evaluate the feasibility and preliminary effects of the music therapy intervention. The usual cognitive rehabilitation program during the subacute stroke period focuses on restoring cognitive abilities such as attention, memory, executive functions, and communication. The key components typically include:

1. Attention Training: Exercises that improve sustained, selective, and divided attention, crucial for regaining concentration in daily activities.

2. Memory Aids: Tools like mnemonic strategies, repetition tasks, and external memory aids (e.g., calendars, notes) help rebuild short-term and working memory.

3. Executive Function Training: Targeting skills such as problem-solving, planning, and organizing tasks through structured exercises, gradually improving independent thinking.

 Communication and Language Therapy: Speech-language pathologists work with patients to improve verbal and non-verbal communication, focusing on both comprehension and expression.
 Problem-Solving Exercises: These help patients break down real-life problems into smaller, manageable steps, encouraging better decision-making skills.

The control group's daily rehabilitation sessions will last for 45 minutes, mirroring the music therapy group's session duration, ensuring a fair comparison of outcomes across both groups. This comparison will help assess the unique contributions of music therapy on cognitive functions like attention, memory, and executive functions in stroke patients.

Inclusion Criteria:

- 1. Diagnosed with ischemic or haemorrhagic stroke confirmed by CT scan
- 2. Duration of stroke within the first 3 months
- 3. Aged 18 75 years old
- 4. Ability to provide informed consent
- 5. Understands Bahasa Melayu or English with basic communication abilities to follow instructions during therapy sessions
- 6. Mild to moderate cognitive impairments with MoCA score of 10-25.

Exclusion Criteria:

- 1. Severe aphasia
- 2. Significant uncorrected hearing or visual impairments preventing engagement in music therapy.
- 3. Severe or unstable medical conditions (e.g., uncontrolled hypertension or diabetes).
- 4. Medications that significantly impair cognition or motor function (e.g., high-dose sedatives).
- 5. History of neurological diseases other than stroke (eg, Parkinson's disease).

Outcome measures

This will be assessed at baseline, after completion of 8 sessions and also at 1 month after completion. Primary outcome measures are Montreal Cognitive Assessment (MoCA), Trail Making Test (TMT), Digit Span (Forward and Backward) and Clock Drawing Test (CDT). The secondary outcome measure is MBI.

Sample size calculation:

A sample of 30 subacute stroke patients (15 control and 15 intervention) will be recruited from the UMMC rehabilitation ward. This number is chosen based on practical considerations to evaluate feasibility metrics and exploratory analysis as in the objectives. For these purposes, a sample size of 30 is typically adequate to gather enough information about the practical aspects of the trial. This number could also ensure that the feasibility objectives are met even with at least 20% dropouts. The average stroke admission to the rehabilitation ward in UMMC is five patients per week, and the number of potential patients that will be eligible is estimated about 2 per week. This total number of 30 will be sufficient within the study period and the grant duration.

Statistical Analysis:

Descriptive Statistics and Exploratory Inferential Statistics will be used in this study.

The means, standard deviations, and 95% confidence intervals (CIs) for cognitive outcome measures (e.g., memory, attention, executive function scores) at baseline, post-intervention, and

follow-up will be used. This will provide a preliminary understanding of the data distribution and effect sizes.

For the exploratory Inferential Statistics, independent t-test (or Mann-Whitney U Test) will be used to compare the mean changes in cognitive scores between the intervention and control groups. The independent t-test if the data are normally distributed. If not, we will use the Mann-Whitney U test as a non-parametric alternative.

Within each group, we will compare the baseline and post-intervention scores using the paired t-test for normally distributed data or the Wilcoxon signed-rank test for non-parametric data. Cohen's d will be used for independent t-tests (between groups) or r for non-parametric tests.

A repeated measures ANOVA (if the data is normally distributed) or a mixed-effects model will be used to explore changes over time (baseline, post-intervention, and follow-up). Given the small sample size, these analyses will likely be underpowered but can provide estimates of variability and preliminary trends.

RESEARCH DATA

Where will the data be kept?

The demographic data of the patients, especially the control group will be kept in the EMR as the usual practise, since they receive neurorehabilitation therapy as a standard care. The additional baseline data for the study, data on cognitive performance and other relevant data will be kept in a separate research file. The files are in the laptop will be secured with password and the notes will be kept in a locker in the Department of Rehabilitation Medicine, Faculty of Medicine with one of the co-researchers.

Anonymity of data

All patients will be identified with a code number and not real names in the research files. The data entry into the excel sheet and into the research thumb drive will follow the similar process.

Who will have access to the research data?

All the co-researchers & research assistant

How long will the data be kept?

7 years

BUDGET / FINANCIAL SUPPORT (IF APPLICABLE):

Grant: Yayasan Penyelidikan Otak, Minda Dan Neurosains Malaysia of RM6,000

GANTT CHART

| | Dec – | March – | July – | Sept – | March | July – |
|---|---------|---------|--------|---------|-------|--------|
| | Feb | June | Aug | Feb | –June | Oct |
| | 2024/25 | 2025 | 2025 | 2025/26 | 2026 | 2026 |
| Development of the project and trial registry | | | | | | |

| 2. Recruitment and randomisation phase | | | | |
|--|--|--|--|--|
| 3. Data entry & analysis | | | | |
| 4. Manuscript writing | | | | |
| 5. Submission for publication | | | | |
| 6. Promote research | | | | |
| outcomes | | | | |

REFERENCES (up to 10 references)

- 1. Thaut, M. H., Gardiner, J. C., Holmberg, D., Horwitz, J., Kent, L., Andrews, G., Donelan, B., & McIntosh, G. R. (2009). Neurologic Music Therapy improves executive function and emotional adjustment in traumatic brain injury rehabilitation. Annals of New York Academy Sciences, 1169, 406-416.
- 2. Thaut, M. H. (2010). Neurologic Music Therapy in cognitive rehabilitation. Music Perception, 27(4), 281-285.
- 3. Yoo, G. E., & Kim, S. J. (2016). Rhythmic auditory cueing in motor rehabilitation for stroke patients: Systematic review and meta-analysis. Journal of Music Therapy, 53(2), 149-177

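### Anonymous codes and a locked allocation file conceal the allocation record, but they do not ensure unbiased assessment at the two follow-up visits

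*Protocol*

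**What the plan says.** Under Study design, the protocol states that "The assessor is blinded to the patients' allocation group and will evaluate the cognitive outcomes at baseline", and at the two later visits. Two measures support this. First, "the group assignments will be kept in a password-protected file that only the study coordinator can access". Second, "the patients will be labelled with anonymous codes that do not reveal whether they are in the control or intervention group". From these it draws its conclusion: "The assessor will only know the code, not the group assignment, ensuring unbiased evaluation".

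Other sections describe the conditions under which that blinding has to hold:

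- **Control group:** standard neurorehabilitation "without the addition of music therapy".
- **Intervention group:** patients learn a percussion rhythm, after which "they sing along with the therapist while playing the rhythm". Sessions last 45 minutes, four times a week for two weeks.
- **Sample size calculation:** all 30 patients "will be recruited from the UMMC rehabilitation ward".
- **Outcome measures:** MoCA, Trail Making Test, Digit Span and Clock Drawing Test, at baseline, after the 8 sessions, and 1 month after completion.
- **Who will have access to the research data?:** "All the co-researchers & research assistant". It is not said whether the assessor is one of these.

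**The concern.** The protocol states a result (unbiased evaluation) and gives a cause for it (the assessor sees only a code). A code can keep an assessor from learning the arm by looking it up. It cannot keep the assessor from learning it from the patient, from ward staff or by observation.

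This matters because objective 3 uses these scores to estimate effect sizes for planning a fully powered trial. If the assessor learns the arm, prompting, timing or scoring could differ between arms. The resulting shift would be part of the estimated effect and could not be separated from it afterwards. As written, the trial also records nothing that would show whether blinding held, although a feasibility trial is a cheap place to find out.

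**Working it through.** The protocol gives no figure for this point, so there is nothing to reproduce. The check sets each route by which the assessor could learn the arm against the measures described.

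| Route to unblinding | Relevant text | Measure described |
|---|---|---|
| Reading the allocation list | Study design | Yes: file open to the coordinator only |
| Reading the arm from the patient's label | Study design | Yes: anonymous code |
| The patient mentions the therapy | Control group, Intervention group: no sham, so patients know what they received | None |
| Ward staff mention it, or a session is seen or heard | Sample size calculation: one ward; Intervention group: singing and percussion, coordinated with the rehabilitation team | None |
| Research data other than the allocation list | Who will have access to the research data? | Not settled: the assessor is neither included nor excluded |

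**Which visits are exposed.** A MoCA score of 10-25 is an inclusion criterion, so at least the baseline MoCA must be scored before randomisation, when there is no arm to disclose. The timing of the other baseline tests is not stated. The exposed visits are the two follow-ups: at most 30 × 2 = 60 assessments, or 24 × 2 = 48 if 20% of patients (30 × 0.20 = 6) are lost before the first of them.

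**How the tests are given.** The mode of administration is not stated. Drawing a clock and completing a trail are tasks performed for an examiner, so face-to-face testing is a strong inference, but still an inference.

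**Size of any bias.** Let p be the share of follow-up assessments in an arm at which the assessor knows the arm, and b the average shift in score when this happens. The bias in the difference between arms is

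p(music) × b(music) − p(control) × b(control),

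divided by the between-patient SD to put it on the scale of Cohen's d. The protocol gives no value for p, b or the SD, so no number can be derived.

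**The case against.** The strongest case on the other side has four parts.

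1. **The protocol does more than use codes.** It restricts the allocation file to the coordinator and assigns delivery and assessment to different roles, a music therapist and a trained assessor. This stands. It does not close the gap, because none of it acts at the moment of testing.

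2. **An assessor from outside the ward could stay blind throughout.** This also stands. A reader might infer that the blinding fails; the document shows only that it is not ensured. It does not say where the assessor works, where sessions or tests take place, or whether patients are still on the ward at the last visit.

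3. **The data-access rule need not include the assessor.** This is right. A reader might infer that the assessor can see music-session attendance and so deduce the arm. The protocol does not say that the assessor is a co-researcher or the research assistant, or where session records are kept. Nor does it say that control attendance goes unrecorded. Study design states that the assessor has no access to the allocation. What remains is a gap to close, not a contradiction.

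4. **The tests are structured, the analysis is exploratory and described as likely underpowered, and disclosure instructions often sit in a study manual.** Structure limits examiner influence, particularly for Digit Span and the timed Trail Making Test, but does not remove it. The exploratory label lowers the stakes, since no confirmatory claim depends on these scores. It does not make the sentence about unbiased evaluation correct, and that sentence is in the protocol itself.

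**Conclusion.** The point holds in a limited form. The codes and the restricted file conceal the allocation record. They do not ensure unbiased evaluation at the two-week and 1-month visits, because patients know their arm and no safeguard at those assessments is described. This rests on two readings: that patients can tell whether they had music sessions, which follows from the absence of a sham, and that they perform the tests for the assessor, which follows from the nature of the tests.

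The size of any bias is unknown. A reader might want to express it as a fraction of a plausible effect, but that would require an assumed score shift, SD and target effect, none of which the protocol gives. Bias in favour of music therapy is the plausible direction, but it is not certain. The trial is not invalidated: this is an overstated assurance that should be corrected because the correction is cheap and the scores feed the planning of the next trial.

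**What to change.** - **Study design, wording:** replace the phrase about unbiased evaluation with a statement that the codes and the restricted file conceal the allocation record from the assessor.
- **Patient instruction:** have the coordinator ask each patient, in both arms and before each follow-up test, not to mention the therapy received. The coordinator already holds the allocation, so nobody new is unblinded.
- **Access:** state that the assessor sees neither allocation nor music-session records until the last assessment is entered. If the assessor falls within the group under Who will have access to the research data?, write this as an exception to that rule.
- **Record:** after each follow-up test, have the assessor note whether the arm was disclosed or became evident, and which arm they would guess. Report both by arm and visit as a feasibility result. Keep them separate: a correct guess may only reflect how well the patient performed, whereas a noted disclosure is direct evidence of unblinding. With at most 30 patients per visit this is a rough check, but it tells the larger trial whether stronger measures are needed.

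The cost is one extra form item at each follow-up, a short instruction to patients and a restriction on file access. No extra staff or patients are needed, and treatment is unchanged.

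### The protocol says matching session length at 45 minutes makes the comparison fair, but music therapy is an add-on worth up to 360 extra scheduled minutes

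*Protocol*

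**What the plan says.** Study design defines the contrast as "an intervention group receiving intensive music therapy in addition to standard neurorehabilitation, and a control group receiving only standard neurorehabilitation". The Control group section agrees: "participants will receive the standard neurorehabilitation program prescribed by the rehabilitation team, without the addition of music therapy".

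The dose of music therapy is in the Intervention group section, item 6: "Each session lasts 45 minutes and is conducted four times a week for two weeks, integrated with the patient's standard neurorehabilitation". Study design places the second assessment at two weeks, after 8 sessions.

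Later in the Control group section, after a list of the usual cognitive rehabilitation components, the protocol says: "The control group's daily rehabilitation sessions will last for 45 minutes, mirroring the music therapy group's session duration, ensuring a fair comparison of outcomes". The next sentence reads: "This comparison will help assess the unique contributions of music therapy on cognitive functions".

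Under Statistical Analysis, an independent t-test or Mann-Whitney test "will be used to compare the mean changes in cognitive scores between the intervention and control groups", with Cohen's d (or r for the non-parametric test) as the effect size. Objective 3 says that effect sizes from this trial will inform a larger, fully powered trial.

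**The concern.** The fairness sentence describes a property that the add-on design does not have. If both arms receive standard rehabilitation, the length of a standard session cannot balance a block of sessions that only one arm receives. A reader of the Control group section would take it that therapy time had been dealt with. A reader of Study design would conclude that it had not.

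What is at stake is the meaning of the effect size. With an add-on, the difference in mean change reflects music therapy plus the extra time spent with a therapist. That is the right quantity for a later trial with the same add-on contrast. It is the wrong quantity for a later trial in which control receives matched sessions, and the fairness sentence invites that use. The objectives on recruitment, retention, adherence and integration, the randomisation, the sample size and the choice of tests are not affected.

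**Working it through.** **Inputs, all from the protocol**
- Music session length: 45 minutes (Intervention group, item 6).
- Frequency and duration: 4 a week for 2 weeks (same item).
- Number of sessions before the second assessment: 8 (Study design).
- Standard rehabilitation: given to both arms (Study design). Total minutes not stated; call this S.
- Control sessions: 45 minutes, daily (Control group). Neither days per week nor sessions per day is stated.

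**Step 1. Reproduce the stated session count.** 4 × 2 = 8, which agrees with Study design.

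**Step 2. Scheduled music time.** 8 × 45 = 360 minutes, or 6 hours over two weeks.

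**Step 3. Difference in scheduled minutes, music arm minus control, under each possible reading**

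| Reading | Calculation | Difference |
|---|---|---|
| Add-on, as Study design states | (S + 360) − S | +360 |
| Substitution, minute for minute | (S − 360 + 360) − S | 0 |
| Matched counterpart sessions, control also four a week | (S + 360) − (S + 360) | 0 |

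The add-on figure does not depend on S. It is an upper limit on what is delivered, because "Rest breaks are included, and the therapist adjusts the session based on the participant's endurance".

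**Step 4. Test each reading against the text**
- *Add-on.* Agrees with Study design and with the description of control. Only the fairness sentence fails.
- *Substitution.* The word *integrated* in item 6 permits it, but it conflicts with the statement in Study design that music therapy is additional. The description of control as standard care only, without music, stays true. Nothing in the protocol names a standard session that is dropped.
- *Matched counterpart sessions.* The word *mirroring* suggests it, but it conflicts with control receiving only standard care. It also fails to match time as written, because control sessions are daily and music sessions are four a week. No section describes an extra control session.

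No reading makes all of these sentences true together. The only one that the arm definitions state outright is the add-on, and under it the difference is up to 360 minutes.

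**The case against.** The strongest reply is that the sentence is literally narrow. It says that one session lasts as long as another, 45 minutes against 45, which is true, and it never says that total therapy time is equal. That is correct as far as it goes. But the sentence then draws a conclusion about fairness from the equal lengths, and under the add-on design that conclusion does not follow.

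A second reply is that contact with the therapist is part of music therapy. The Intervention group section closes by describing the approach as working "by integrating music, rhythm, and therapeutic interaction into the neurorehabilitation process". This stands. The sentence on unique contributions is defensible if added contact counts as part of the treatment. It misleads only if read as an effect over and above contact time, and the fairness sentence just before it encourages that reading.

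A third reply is that the efficacy analysis is exploratory and acknowledged to be underpowered. This also stands, and it limits the severity. It does not remove the point, because Objective 3 gives the effect size a use beyond this trial.

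A reader might infer more than the documents support:
- *A percentage excess.* If standard care were one 45-minute session a day on 5 to 7 days a week, S would be 450 to 630 minutes and 360 would be 80% to 57% extra. With two sessions a day, S would be 900 to 1,260 minutes and 360 would be 40% to 29% extra. The protocol fixes neither schedule, so no percentage belongs in the conclusion.
- *That the design is unsound.* Add-on against usual care is a normal feasibility contrast, and nothing here argues against it.
- *That all the control wording is wrong.* Under substitution only the statement that music is additional would need to change.

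**Conclusion.** The fairness statement is wrong as written. As the arms are defined, the music arm is scheduled for up to 360 more therapy minutes over two weeks, so equal session length does not make therapy time equal. The between-group effect size estimates music therapy together with that added time.

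The 360 follows from the protocol's own figures and rests on the add-on reading, which Study design states and the description of control supports. It is scheduled time; delivered time may be lower. If the investigators in fact mean substitution or matched sessions, the difference could be zero, but then the definition of the arms is what needs correcting. Severity is minor to moderate: the error affects how an exploratory effect size may be interpreted and reused, not the conduct of the feasibility work.

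**What to change.** State once, in Study design, whether music sessions add to or replace standard sessions. Then:

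- **If they add.** In the Control group section, delete the part of the sentence that begins at *mirroring* and claims a fair comparison across the groups. Add: The contrast, and the effect size carried to the larger trial, is music therapy with its extra contact time plus standard rehabilitation, against standard rehabilitation alone. With that in place, the sentence on unique contributions can no longer be read as a time-matched effect.
- **If they replace.** Correct the statement in Study design that music therapy is additional, and name the standard sessions replaced.
- **If control is meant to have matched counterpart sessions.** Correct *only* in Study design, describe those sessions, and give control the same four a week in place of *daily*.

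The cost is a few sentences of text and, for the add-on, a narrower statement of what the effect size shows. Recording the minutes delivered in each arm would help interpretation but is optional; correcting the error does not require it.

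### A normality check in 12 to 15 patients per arm picks both the test and the effect scale, so Cohen's d and r may be mixed across scores and visits and are harder to carry into the larger trial

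*Protocol*

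**What the plan says.** The Statistical Analysis section of the Protocol plans two layers. The first is descriptive: mean, SD and 95% CI of the cognitive measures at baseline, post-intervention and follow-up, with no condition attached. The second is exploratory inference, where an "independent t-test (or Mann-Whitney U Test) will be used to compare the mean changes in cognitive scores between the intervention and control groups". The choice between the two tests is conditional: "The independent t-test if the data are normally distributed. If not, we will use the Mann-Whitney U test as a non-parametric alternative". The effect measure is tied to that choice: "Cohen's d will be used for independent t-tests (between groups) or r for non-parametric tests". The within-group tests and the longitudinal model also depend on normality.

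The Sample size calculation section gives the numbers: "A sample of 30 subacute stroke patients (15 control and 15 intervention) will be recruited from the UMMC rehabilitation ward". The figure is practical ("This number is chosen based on practical considerations to evaluate feasibility metrics and exploratory analysis as in the objectives") and is said to suffice so that "feasibility objectives are met even with at least 20% dropouts". Outcome measures lists MoCA, TMT, Digit Span forward and backward, and CDT as primary, assessed at baseline and at two later visits. Objective 3 gives the purpose of the cognitive data: effect sizes for designing a fully powered trial.

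**The concern.** The rule is fixed in the Protocol itself; it is not a detail left to an unseen SAP. It does two things that work against Objective 3.

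- **It changes what is estimated.** Both tests are said to serve "to compare the mean changes in cognitive scores between the intervention and control groups". The t-test does that. Mann-Whitney compares ranks, not means.
- **It changes the reported scale.** One score may be summarised as d and another as r, or the same score as d at one visit and r at the next. On the rank branch, no CI for the between-arm difference and no SD of change is promised, and these are what the planner of a change-score or baseline-adjusted trial would look for.

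At this sample size the branch is a weak guide to the true shape of the data. Scores recorded in whole points can fail a normality check even when the underlying scale is normal.

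**Working it through.** **Inputs from the Protocol.** 15 per arm; 20% dropout leaves 15 × (1 − 0.20) = 12 per arm. Five cognitive scores if TMT counts once, and two post-baseline visits. The sample size of 30 is a practical choice, so there is no power figure to reproduce.

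**Assumptions.** The Protocol names no normality check. Two were simulated: Shapiro-Wilk at 5% in each arm, switching if either arm fails, and one Shapiro-Wilk test on pooled within-arm residuals. The shapes of the change scores are also assumed, as is a comparison at both later visits.

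**Step 1: chance that one comparison switches to Mann-Whitney, 15 per arm**

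| Change score | Either-arm check | Pooled residuals |
|---|---|---|
| Exactly normal | 9-10% | 5% |
| Normal, rounded to whole points, SD 2 | 24-25% | 11% |
| Lognormal, sigma 0.5 | 62-65% | 67% |

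The ranges in the either-arm column come from repeated simulations. At 12 per arm that check gives about 9%, 23% and 49-51%. For whole-point changes with SD 1 it gives 63-65% at 12 per arm and 81-82% at 15.

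**Step 2: chance that five scores at one visit end on mixed scales.** With switch rate q and scores treated as independent, this is 1 − q^5 − (1−q)^5.

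- q = 0.05: 1 − 0.774 = 0.23; q = 0.10: 1 − 0.590 = 0.41.
- q = 0.11: 1 − 0.558 = 0.44; q = 0.25: 1 − 0.001 − 0.237 = 0.76.
- q = 0.62: 1 − 0.092 − 0.008 = 0.90; q = 0.67: 1 − 0.135 − 0.004 = 0.86.

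Over ten comparisons of exactly normal data, at least one switches with probability 1 − 0.95^10 = 0.40 to 1 − 0.90^10 = 0.65. Real scores are correlated, so these are guides only.

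**Step 3: Type I error of the two-stage rule** (either-arm check). It stayed between 4.4% and 5.6% in every shape simulated. There is no material inflation.

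**Step 4: what visit-level SDs leave open.** With equal visit SDs, SD of change = visit SD × √(2(1−ρ)), where ρ is the baseline-to-follow-up correlation. For an assumed ρ of 0.3 the factor is √1.4 = 1.18; for 0.9 it is √0.2 = 0.45. The variance ratio is 1.4/0.2 = 7, so a change-score sample size could differ sevenfold depending on a quantity the plan does not promise to report.

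**Step 5: gain from baseline adjustment over change scores.** With equal variances the variance ratio is (1−ρ²)/(2(1−ρ)) = (1+ρ)/2, times about 1 + 1/(2n−4) for estimating the slope. That factor is 1.050 at n = 12 and 1.038 at n = 15.

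- ρ = 0.5: 0.75 × 1.050 = 0.788 and 0.75 × 1.038 = 0.779, a reduction of 21-22%.
- ρ = 0.7: 0.85 × 1.050 = 0.893 and 0.85 × 1.038 = 0.883, a reduction of 11-12% (11-13% allowing for simulation).
- ρ = 0.9: 0.95 × 1.050 = 0.998 and 0.95 × 1.038 = 0.986, essentially none.

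**The case against.** A reader might infer that the results could not be compared or carried forward at all. The Protocol does not support that. Visit-level means, SDs and CIs are planned whatever the normality result, so a mean difference and a standardised effect can be derived. Also, r converts approximately to d by 2r/√(1−r²): in simulated normal data with true d of 0.2, 0.5 and 0.8, the converted values averaged 0.21, 0.51 and 0.83. Both points stand, with limits. The descriptives are per visit, reporting by arm is implied rather than stated, and the conversion was checked on normal data, whereas the rule produces r when the data look non-normal.

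A reader might also infer that chance alone sets the test. It does not: the switch rate rises with departure from normality. Nor is the baseline thrown away. Change scores use it, validly under randomisation, though inefficiently unless the correlation is high. The choice of test is not simply left open after the results either: the rule is stated in advance, and its criterion may sit in an SAP.

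Finally, the inference is declared exploratory and likely underpowered, and no decision depends on the test chosen. At 15 per arm the 95% CI for d is roughly ±1.96 × √(2/15) = ±0.72, wider than any gap between d and r. That limits the importance of the point. It excuses low power, but it is no reason to let the effect scale vary.

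**Conclusion.** The point holds in a limited form. The rule makes the reported effect scale depend on the data and can mix d and r across scores and visits, which makes the estimates harder to use for Objective 3. At 15 per arm the switch rate per comparison is about 5-10% for exactly normal data, 11-25% for whole-point changes with SD 2, and 62-67% for lognormal data. These figures rest on assumed checks and shapes. The claim does not extend to invalid tests, an inflated false-positive rate or unusable results. What is missing on the rank branch is a promised CI for the between-arm difference and an SD of change. The remedy uses data already collected, so the change is worth making even in an exploratory trial.

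**What to change.** Drop the normality switch and pre-set one between-group analysis for every score:

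- Regress the follow-up score on arm with the baseline score as covariate. Report the adjusted mean difference with 95% CI, the SDs and the baseline-to-follow-up correlation for all scores.
- Decide in advance whether TMT times are logged.
- Use one standardised effect for all scores and state its SD, preferably the pooled follow-up or residual SD. The baseline SD is unsafe for MoCA because entry is restricted to 10-25, which can compress it and inflate the effect.
- Keep rank or permutation tests as a labelled sensitivity analysis.

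With one pre-set estimator, the chance of mixed scales falls to zero. The cost is analysis wording and one degree of freedom per model; no patients or visits are added. The downside is some reliance on a linear model for coarse scores such as CDT, which the sensitivity analysis is there to examine. The precision gain depends on the correlation, which the Protocol does not give.
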